Principal investigators and participating centers	[name] Psychiatry Hospital of Santa Creu i Sant Pau [name]: Hospital del Mar. Barcelona [name] : Reina Sofia University Hospital. Cordova [name] : Parc Taulí University Hospital [name] : A Coruña University Hospital [name]: Gregorio Marañoñ University Hospital, Madrid [name]: University of Navarra Clinic. Pamplona [name] : Hospital Clínic, Barcelona [name]: León University Assistance Complex [name]: Valle del Nalón Hospital. Asturias [name]: Vigo University Hospital Complex, Pontevedra [name]: Arnau de Vilanova University Hospital. Lleida [name]: San Carlos Clinical Hospital, Madrid [name]: Bellvitge University Hospital [name]: Hosp. Univ. Virgen del Rocio of Seville [name]: Regional University Hospital of Malaga

	
[name]: Germans Trias i Pujol University Hospital. badalona [name] : Virgen de la Macarena Hospital, Málaga [name] : Hospital Mutua de Terrassa, Terrassa. [name] : Son Llàtzer Hospital, Majorca [name]: Trueta Hospital, Girona [name] : University Hospital of the Canary Islands, Tenerife. [name] :H. Virgin of Light-Cuenca [name] : H. University Virgen de la Victoria-Málaga. [name] : Reina Sofia-Córdoba University Hospital [name] : Viladecans Hospital, Barcelona [name] : H. University [name]: [name] : H. San Carlos Clinic in Madrid [name] : H. de Reus [name] : H. General of Vic

Reference ethics committee	CEIM of the Hospital de la Santa Creu i Sant Pau
Main goal	To study the evolution after bariatric surgery in patients with obesity and schizophrenia
Design	Multicenter retrospective case control study.
Disease under study	Schizophrenia and Obesity
Methodology	Retrospective observational study
Study population and total number of subjects	Cases: Patients with schizophrenia and obesity undergoing bariatric surgery. (number: all cases collected within the GOSEEN group). Controls: Patients without psychiatric pathology matched by age, sex, BMI and type of surgery and in a 4:1 ratio to cases.
Calendar. Expected duration of the study.	12 months

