Justification

It is necessary to have information about the prognosis of subjects with severe obesity and schizophrenia who undergo bariatric surgery. This knowledge will make it possible to establish clear guidelines for action in these cases.

Research questions

What is the long-term outcome after bariatric surgery in subjects with schizophrenia?

Hypothesis

Bariatric surgery in subjects with schizophrenia leads to an improvement in weight and cardiometabolic comorbidities similar to that of subjects without schizophrenia

3. GOALS:

Main goal:

To study the short (first year after bariatric surgery) and long-term (up to 5 years of follow-up after bariatric surgery) evolution in terms of weight loss of patients with obesity and schizophrenia who underwent bariatric surgery in Spain and compare it with the evolution of patients without psychiatric disorder.

Secondary objectives:

- Determine the casuistry of patients, with special interest in the characteristics of the underlying psychiatric pathology (years of evolution, clinical stability criteria, pharmacological treatment...).
- To Analyze the evolution of obesity comorbidities.
- To Analyze the evolution of psychiatric pathology after bariatric surgery: (decompensation, drug treatment...)
- To analyze the frequency of early (<30 days post-surgery) or late (>30 days post-surgery) post-surgical complications.

4. METHODS:

Study design

Retrospective case-control study.

Study population. Inclusion, exclusion criteria

Cases:

Inclusion) Both criteria must be met:

- 1.- Patients with severe obesity undergoing bariatric surgery and with follow-up in Spanish territory.
- 2.- Patient with schizophrenia or schizoaffective disorder.

Exclusion)

Subjects who do not meet any of the two inclusion criteria

Controls: in a 4:1 ratio with cases

Inclusion) Both criteria must be met:

- 1.- Patients with severe obesity undergoing bariatric surgery and with follow-up in Spanish territory.
- 2.- Absence of psychiatric pathology
- 3.- Paired with the cases by age, sex, BMI before surgery and type of surgery.

Exclusion)

Subjects who do not meet any of the two inclusion criteria

Definition of variables

Main variables:

- weight
- size
- BMI

- TWL (total weight loss)
- EWL (excess weight loss)

Secondary variables:

- Age, ethnicity, educational level
- Type of surgery
- psychiatric dx
- Years of evolution of the psychiatric disorder at the time of IQ
- Psychiatric drug treatment, lithium, medication load.

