- Number of psychiatric admissions prior to IQ.
- Number of psychiatric admissions/psychiatric emergencies after surgery (relapses): In-hospital relapses, Relapses < 30d, relapses during follow-up.
- Criteria for approval of surgery (in each center).
- Biochemical parameters: glucose, HbA1c, total cholesterol, triglycerides, HDL, LDL.
- Early and late postoperative complications and death of the patient.
- Presence of diabetes, arterial hypertension, dyslipidemia, OSAS and liver disease and treatments for these pathologies.
- Adherence to follow-up in endocrinology and dietetics (Number of visits attended/Number of scheduled visits)
- Lost to follow-up.

The collection of variables will be carried out pre-surgery and 1 month, 6 months, 12 months and subsequently annually until a maximum of 5 years of follow-up.

Expected sample size

All cases detected in Spanish territory

The minimum number of cases expected will be 10 patients based on the low casuistry of the problem. The number of patients in the control group will be x4 that in the study group.

Methodology. Information sources

The study population will be identified in each center in the usual specialty consultations or by searching the databases of each center. Review of medical records in search of the specified variables (retrospective observational study).

Data Management and Analysis

The coordinating researcher (Dra [name]) will be responsible for the creation of the database and its exploitation. The database will be created in Excell format and the SPSS program will be used for statistical analysis. The statistics will be mainly descriptive. For cases in which it is decided to compare groups, normality tests will be used to establish the behavior of the variables and parametric/non-parametric tests will be used as appropriate.

Data collection

The researcher will guarantee the accuracy and integrity of the data, as well as all the reports that are required. The data included in the Data Collection Notebook (CRD), which are derived from source documents, will be consistent with those documents or otherwise the discrepancies will be justified.

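### The control criterion on psychiatric status has no reference date, so controls can be excluded for diagnoses first made after surgery

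*Protocol*

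**What the plan says.** In the protocol's Methods, under Study population, the second control criterion is "Absence of psychiatric pathology". The third is "Paired with the cases by age, sex, BMI before surgery and type of surgery". Within this list BMI is tied to a time before the operation and psychiatric status is not. The synopsis is no more specific: "Patients without psychiatric pathology matched by age, sex, BMI and type of surgery and in a 4:1 ratio to cases". The main goal describes the comparison group as free of psychiatric disorder, also without a date.

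The section on information sources says how subjects are found: "The study population will be identified in each center in the usual specialty consultations or by searching the databases of each center". Their records are then reviewed. Variables are collected from before surgery up to a maximum of 5 years afterwards. The evaluation scheme in Appendix 1 places the eligibility check at V0, in the same column as collection of the post-surgical course.

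For cases the criterion is "Patient with schizophrenia or schizoaffective disorder", again undated. Psychiatric admissions and emergencies after surgery are listed among their variables, and the course of the psychiatric illness after surgery is a secondary objective.

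**The concern.** The main goal compares weight change after surgery between two groups, so membership of each group should be settled by what was known at surgery. In a prospective study an undated criterion would do little harm, because the later years would not yet exist when eligibility was judged. Here they may already be in the record, and nothing tells the person reading it to stop at the date of surgery.

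A control who was well at surgery but was diagnosed with, say, depression in year 2 does not meet the criterion as worded. Rejecting that patient selects controls on an event inside the outcome period. Cases face no matching filter, since their later psychiatric events are counted as results.

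If patients who develop psychiatric illness after surgery tend to lose less weight, the remaining controls are a group chosen partly for a good course. Patients with schizophrenia would then look worse by comparison than they should. The many centres listed in the synopsis could also read the line differently, so the selection could vary between sites.

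**Working it through.** **Is there a cut-off anywhere?** Taking the relevant places in turn:

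| Place in the protocol | Reference date for psychiatric status |
|---|---|
| Synopsis, controls | none |
| Main goal, comparison group | none |
| Methods, control criterion 2 | none |
| Methods, control criterion 3 | dates BMI only |
| Information sources | none; retrospective record review |
| Appendix 1 | eligibility at V0, together with post-surgical data |

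No entry stops a diagnosis made after surgery from excluding a control. No entry tells sites to use such a diagnosis either.

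**The plan's own figures.** The protocol gives a minimum of 10 cases and four controls per case: 10 × 4 = 40 controls, 50 subjects in all. It states no effect size, standard deviation or power, so there is no calculated figure to reproduce.

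**Size of the shift (illustration, assumed inputs).** Let p be the share of otherwise eligible controls first diagnosed after surgery. Let d be how many percentage points less total weight they lose than the other controls.

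- Mean with all eligible controls kept = (mean of the others) − p × d.
- Mean with those controls screened out = mean of the others.
- Upward shift from screening = p × d.

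With p = 10-25% and d = 3-6 points:

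- low end: 0.10 × 3 = 0.3 points
- high end: 0.25 × 6 = 1.5 points

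With a wider range, p = 5-30% and d = 2-8 points:

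- low end: 0.05 × 2 = 0.1 points
- high end: 0.30 × 8 = 2.4 points

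**Against sampling error.** The standard error of the difference, treating the groups as independent, is SD × √(1/10 + 1/40) = SD × 0.354. With an assumed SD of 8-10 points this is 2.8-3.5 points. At the minimum size the shift is therefore smaller than the noise.

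The protocol seeks all cases, however, and 10 is only a floor. With 40 cases and 160 controls the factor is √(1/40 + 1/160) = 0.177, and the standard error falls to 1.4-1.8 points. The shift stays at p × d whatever the sample size.

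**The case against.** The strongest reply is that silence is not an instruction. The protocol nowhere says that a control's whole record is to be screened, and a sensible site might judge psychiatric status at the pre-surgical evaluation. A reader might infer that controls are in fact screened on their outcome years. The text does not support that; it only leaves it open. This part of the reply stands, and the point is limited to what the criterion allows.

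A reader might also infer that a schizophrenia diagnosis first made after surgery can define a case, with the first episode then counted as a relapse. The case criterion is undated too, but the surrounding text points firmly the other way. The synopsis speaks of "Patients with schizophrenia and obesity undergoing bariatric surgery". The variables include "Years of evolution of the psychiatric disorder at the time of IQ" and "Number of psychiatric admissions prior to IQ", where IQ evidently means the operation, and later events are called relapses. All of this presumes illness before surgery. None of it is an eligibility rule, so a clarifying phrase is useful, but it does not make a finding about cases, and no effect on relapse frequency should be claimed.

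Two further replies concern importance. The sizes rest wholly on assumed inputs and, at 10 against 40 in a mainly descriptive study, would not be visible. Also, flattering the controls makes similarity harder to show, so this problem would not by itself produce a finding of similarity. Both are right. But the bias is systematic, it remains as cases accrue, and it could make bariatric surgery in schizophrenia look less effective than it is, in a study meant to inform guidance.

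The protocol does name its retrospective nature as the main limitation, but that general statement does not address selection on later diagnoses.

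An unseen analysis plan would not cure the gap. Sites apply eligibility when they identify patients, and an analysis plan cannot bring back controls who were never entered.

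**Conclusion.** The point holds for controls. Their psychiatric criterion has no reference date, it is applied to records that can already contain the outcome years, and nothing in the protocol prevents a post-surgical diagnosis from excluding a control. Cases keep their later psychiatric events, so the selection is one-sided.

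The direction, against the hypothesis of similar improvement, depends on later psychiatric morbidity going with poorer weight loss, which the documents do not establish. The size cannot be derived from the documents. The 0.3-1.5 points (0.1-2.4 on wider inputs) illustrate what assumed inputs would give and are not an estimate. The matter is worth correcting because it concerns who enters the comparison and costs almost nothing to put right. It does not show that the comparison is already biased. For cases, only a wording note remains.

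**What to change.** - **Controls:** define them as having no psychiatric diagnosis documented up to and including the date of surgery.
- **Later diagnoses in controls:** state that a diagnosis first made after surgery does not exclude a control. Keep these patients in the analysis and record the diagnosis and its date as a follow-up event.
- **Cases (wording note):** add that the diagnosis of schizophrenia or schizoaffective disorder is documented on or before the date of surgery, as the protocol's own variables already presume.

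The cost is two eligibility lines and one follow-up item for controls, with no extra patients or visits. If sites have already selected controls, they should check whether any were rejected for a diagnosis first made after surgery. The small downside is that some controls will develop a psychiatric disorder during follow-up, so the comparison group will be free of psychiatric illness at surgery but not throughout. The report should say so.

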ethical considerations	Informed consent will be obtained from patients who are currently being followed up at the reference centers.
Funding source	Not precise

2. THEORETICAL FRAMEWORK. PROBLEM STATEMENT:

Background

Obesity affects approximately 45-55% of patients with schizophrenia (1). Weight gain in these patients may be due to different factors such as the use of antipsychotic drugs with an unfavorable metabolic profile, the coexistence of sleep disorders or negative cognitive symptoms that often translate into a more sedentary lifestyle and alterations in eating behavior, among others (2). The coexistence of obesity and its comorbidities in this group of patients significantly worsens both their physical and mental health (3). In fact, cardiovascular disease is one of the main causes of mortality in patients with schizophrenia (4).

Lifestyle interventions, while they may be effective in people with schizophrenia (5), often fall short of achieving weight goals. At present, obesity surgery represents the most effective treatment in terms of weight loss and resolution of comorbidities, being indicated in cases of patients with a body mass index (BMI) > 35 kg/m² with comorbidities or BMI > 40 Kg/m² with/without comorbidities. However, the access of patients with schizophrenia to bariatric surgery techniques is usually limited by different factors such as fear of a possible worsening of the underlying disease, or a lower weight loss in this population, among others. In addition, clinical practice guidelines recommend that all patients with psychiatric pathologies be evaluated in a regulated manner prior to surgery (6), although the content of this evaluation and the criteria for declining or accepting surgery are not clear. Although the course of schizophrenia is variable and its symptoms may be stable without being a clear contraindication for bariatric surgery, in actual practice, a considerable number of professionals contraindicate bariatric surgery in the presence of a psychotic disorder (7).

For these reasons, data on the efficacy of bariatric surgery in patients with schizophrenia are scarce and limited to very small case series with short-term follow-up (2,8,9). Our objective is therefore to carry out a multicenter retrospective study that allows us to study the long-term evolution after bariatric surgery in a large series of patients, focusing not only on weight evolution but also on the long-term evolution of psychiatric pathology.

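### The main goal is a case-control comparison of weight loss with a hypothesis of similarity, but no measure, visit or criterion for similar is fixed, and a non-significant test could pass as similarity

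*Protocol*

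**What the plan says.** - **Main goal (Protocol, section 3).** The aim is "To study the short (first year after bariatric surgery) and long-term (up to 5 years of follow-up after bariatric surgery") in terms of weight loss, and to "compare it with the evolution of patients without psychiatric disorder". Both horizons are periods, not visits.
- **Research question, Background and Hypothesis (section 2).** The question is long-term: "What is the long-term outcome after bariatric surgery in subjects with schizophrenia". The Background speaks of wanting to "study the long-term evolution after bariatric surgery in a large series of patients". The hypothesis is that surgery "leads to an improvement in weight and cardiometabolic comorbidities similar to that of subjects without schizophrenia". No size of difference that would still count as similar is given.
- **Main variables (section 4, Definition of variables).** Weight, height (translated as size), BMI, "TWL (total weight loss") and EWL are listed at one level. TWL has no scale (kg or percent), EWL has no reference weight, and none is tied to a horizon.
- **Collection times (section 4, Definition of variables).** Data are taken "pre-surgery and 1 month, 6 months, 12 months and subsequently annually until a maximum of 5 years of follow-up". None of these times is marked as the short- or long-term assessment.
- **Analysis (section 4, Data Management and Analysis).** "The statistics will be mainly descriptive. For cases in which it is decided to compare groups", normality is checked and parametric or non-parametric tests are used. Intervals are not mentioned.
- **Size (section 4, Expected sample size).** At least 10 cases are expected, with four controls per case.

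**The concern.** The main goal and the 4:1 matched controls make sense only if the groups are compared. Yet the protocol does not say on which measure or at which visit, and the one sentence about comparing groups makes it depend on a later decision. The study reviews existing records, so every outcome is already fixed when that decision is taken.

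The hypothesis makes this more serious. When a study sets out to show a difference, a non-significant test leaves the claim unproven. When it expects similarity and offers only difference tests, a non-significant test looks like success, and the smaller the sample, the easier that is to obtain. The protocol names lower weight loss as one of the fears that limit access to surgery and wants its results to support clear guidelines. A real deficit reported as similarity would therefore matter.

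**Working it through.** **Inputs from the protocol.** Minimum 10 cases and a 4:1 ratio, hence 10 × 4 = 40 controls. The minimum is justified by the rarity of the condition, so there is no power calculation to reproduce.

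**Assumptions (the protocol gives none).** Two-sided alpha 0.05; SD of %TWL 8 points at 12 months and 10 points at 60 months; a true deficit of 8 points for illustration, with 5 points as an alternative; unpaired t-test.

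**Step 1: what is left open.** Four of the main variables can serve as outcomes (weight, BMI, TWL, EWL; height cannot). Post-surgery times are 1, 6 and 12 months and then 2, 3, 4 and 5 years, which makes seven: three in the first year and four after it. That gives 4 × 3 = 12 candidate comparisons for the short term and 4 × 4 = 16 for the long term.

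**Step 2: precision at the minimum size.** Half-width of the 95% CI in SD units = t(0.975, 48 df) × √(1/10 + 1/40) = 2.011 × 0.3536 = 0.711.
- SD 8: 0.711 × 8 = 5.7 points of %TWL.
- SD 10: 0.711 × 10 = 7.1 points.

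Even an observed difference of exactly zero would be compatible with a deficit of this size.

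**Step 3: how often a real deficit would be non-significant.** Non-centrality = (deficit/SD)/0.3536, referred to the non-central t distribution with 48 df.

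| True deficit | Visit (assumed SD) | Non-centrality | Chance of p ≥ 0.05 |
|---|---|---|---|
| 8 points | 12 months (8) | 1.0/0.3536 = 2.83 | 21% |
| 8 points | 60 months (10) | 0.8/0.3536 = 2.26 | 40% |
| 5 points | 12 months (8) | 0.625/0.3536 = 1.77 | 59% |
| 5 points | 60 months (10) | 0.5/0.3536 = 1.41 | 72% |

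**Step 4: sensitivity to the number available.** The 95% half-width is √(1/n + 1/4n) × t:
- 20 vs 80: 0.25 × 1.984 = 0.50 SD, or 4.0 to 5.0 points.
- 30 vs 120: 0.204 × 1.976 = 0.40 SD, or 3.2 to 4.0 points.
- 5 vs 20, if only half of the minimum reached 60 months (assumed): 0.5 × 2.069 = 1.03 SD, or 10.3 points at SD 10.

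An analysis that respects the matched sets would narrow these intervals to the extent that the matching factors explain weight loss.

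**The case against.** Several points on the other side are fair.

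- **The conditional sentence may not concern the main goal.** It covers all variables, many of which exist only in cases (years of illness, psychiatric admissions), and the English is a rough translation. A reader might infer that the main comparison has been made optional. The documents do not establish that, since the main goal says plainly that the groups will be compared. What stands is that the two sections need to agree.
- **A reader might infer that the open choice of measure greatly inflates false positives.** The figures do not support this. In simulations at 10 vs 40 with no true difference, choosing between TWL and EWL at 12 months alone leaves the error at about 5%. Using %TWL alone at 12 and 60 months gives 9 to 10% (1 − 0.95² = 9.75% if independent), and adding EWL at both visits leaves it at about 9 to 10%. Most of the excess over 5% comes from having two horizons, which the main goal itself sets. No firm upper limit can be given for all 28 candidates, because it depends on unknown correlations and on the analysis.
- **Nor does the open choice explain most of the missed deficits.** With an 8-point deficit and %TWL alone at 12 and 60 months, at least one of the two results is already non-significant 45 to 50% of the time at 0.05. Small numbers and two horizons drive this. Naming the measure would not remove it; judging by the interval addresses it.
- **Ten is a minimum.** The protocol seeks all cases across many centres, and Step 4 shows how precision improves. Rarity justifies the size, which is not itself an error.
- **The goal is evolution over time, and detail may sit in an analysis plan that is not shown.** A trajectory can be kept as supportive analysis. Test details and any split of alpha can be left to that plan. But the protocol has its own section on main variables, and that section leaves the main outcome and its timing open.

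**Conclusion.** The point holds as a defect in how the main comparison is fixed. The protocol commits to a comparison and a hypothesis of similarity, but it ranks no measure, assigns no visit to either horizon, states no difference that would count as similar, and offers only difference tests in conditional wording. With outcomes already in the records, measure and visit can be chosen after the fact, and p > 0.05 can be presented as similarity.

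The size of the problem is best expressed by how little a non-significant result would show at the stated minimum: a 95% half-width of 5.7 to 7.1 points of %TWL, and a 21% (12 months) or 40% (60 months) chance of missing a true 8-point deficit. These figures rest on the assumed SDs of 8 and 10, alpha of 0.05, the assumed deficit and full data on 10 cases and 40 controls. They improve with more cases and worsen with loss to follow-up. They measure the weakness of a difference test as evidence of similarity, not the harm done by the choice among measures. The change should be made, but it does not call the design or the data collection into question.

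**What to change.** By written amendment before data extraction, or dated and openly declared if extraction has begun, and with the same wording in the ISRCTN registration:

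1. Name the main measure: %TWL = 100 × (pre-surgery weight − weight at the visit) / pre-surgery weight.
2. Name 12 months as the short-term visit and one stated visit as the long-term one, for example 60 months, reporting how many cases and controls are available there.
3. Replace the conditional sentence in Data Management and Analysis with a statement that cases and controls will be compared on %TWL at these two visits, giving the difference with its confidence interval.
4. State that similarity will be judged from that interval against a difference in %TWL points that the investigators set in advance, and not from p > 0.05.
5. Treat weight, BMI, EWL, the other visits and the trajectory as supportive. The remaining statistics can stay mainly descriptive.

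Whether and how to divide alpha between the two horizons can be left to the statistician.

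The cost is wording only, since all the values are already to be collected. In exchange, other measures and visits can no longer carry the headline, and with only 10 cases the honest conclusion may be that the comparison is inconclusive.

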It is the responsibility of the investigator to obtain the informed consent of the patient. The patient will not be able to participate in any study-specific procedure without obtaining their consent, or that of their legal guardian/family member when the patient is unable to give consent due to their clinical situation.

Before including any subject in the study and before obtaining informed consent, the investigator or the person designated by the investigator will explain to the potential participating subject or their legal guardian/family member the objectives, methods, and potential risks of the study and any inconvenience it may cause. The explanation about the nature, scope and possible consequences of the study will be made in an understandable language.

The prospective participant or their legal guardian/family member should have time to consider their decision to participate in the study, and have the opportunity to ask questions. After this explanation, and before entering the study, the consent must be properly recorded by the signature of the subject or their legal guardian/family member. Given the retrospective nature of the study, it is likely that some patients to be included have died or are no longer seen at their referral center. In this case, informed consent will not be obtained, but the research team undertakes to verify that there is no record of the subjects' express opposition in the clinical history and to comply with the confidentiality regulations.

In addition, since the use of pseudonymized personal data for biomedical research purposes requires technical and functional separation between the research team, and those who perform the pseudonymization and keep the information that enables re-identification, the person who performs the pseudonymization for this study does not will be part of the research team.

For access to the pseudonymous data, an express commitment of confidentiality and not to carry out any re-identification activity is sent, and that specific security measures will be adopted to avoid re-identification and access by unauthorized third parties.

The Model Patient Information Sheet and the Consent Form are presented as an Annex.

Considerations on the treatment of biological samples

Does not apply

Data confidentiality

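### No collected item shows whether, where or until when a case's psychiatric record was seen, so post-surgery relapses may be missed and look the same as none

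*Protocol*

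**What the plan says.** Section 4 (Methods), Definition of variables, lists the relapse outcome among the secondary variables: "Number of psychiatric admissions/psychiatric emergencies after surgery (relapses"), split into events in hospital, events within 30 days and events later in follow-up. The pre-surgery counterpart is "Number of psychiatric admissions prior to IQ". Collection runs before surgery, at 1, 6 and 12 months, and "subsequently annually until a maximum of 5 years of follow-up".

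Under Methodology, Information sources, two sentences cover where things come from. The first is about finding patients: "The study population will be identified in each center in the usual specialty consultations or by searching the databases of each center". The second is about obtaining data: "Review of medical records in search of the specified variables (retrospective observational study"). The second does not say whose records are reviewed.

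Two listed variables bear on how long a patient was observed. One is "Lost to follow-up", with no statement of which follow-up is meant. The other is an attendance ratio that covers endocrinology and dietetics only.

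Section 6, on consent, says "it is likely that some patients to be included have died or are no longer seen at their referral center"; such patients are still included, without consent. The limitations paragraph of section 4 names only the retrospective nature of the study.

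**The concern.** Relapse is known only from events that someone finds in a record. For weight, a missed visit leaves a visible gap. For an admission, silence in the record has two meanings: nothing happened, or it happened where the reviewer could not look. To tell them apart one must know whether a psychiatric record was available and for how long. The protocol collects neither fact.

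The existing follow-up items do not fill the gap. A patient can attend every endocrinology visit for 5 years, be complete for weight, and have been admitted to a psychiatric ward elsewhere. Nothing on the variable list would reveal this, and correcting for the length of bariatric follow-up would not help.

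The stake is the secondary objective on psychiatric evolution after surgery. The background section gives fear of worsening illness as one reason why these patients have limited access to surgery, so an under-counted relapse frequency would err towards reassurance on a question that the study was set up to inform.

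**Working it through.** **The plan's own figures.** The only arithmetic in the protocol is the minimum of 10 cases with four controls each: 4 × 10 = 40 controls, 50 patients in all. This reproduces and is not in dispute. The protocol states no relapse rate, power or alpha. The relapse proportions and capture fractions below are therefore assumptions.

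**What the variable list can distinguish.** Take two cases, both attending the centre for 5 years.

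| | Case A | Case B |
|---|---|---|
| Truth | no relapse | one admission at another hospital |
| Endocrinology/dietetics adherence | full | full |
| Lost to follow-up | no | no |
| Relapse events found, if the outside record was not reviewed | none | none |

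The two rows of data are identical. An item recording whether the psychiatric record was seen would separate a confirmed zero from an unknown.

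**Effect on the absolute post-surgery frequency.** Suppose unseen events are counted as none. Let p be the true proportion of cases with at least one relapse, and m the fraction of relapsing cases whose events all lie outside the reviewed records. Then observed proportion = p × (1 − m).

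With p = 0.40:

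- m = 0.10: 0.40 × 0.9 = 0.36, or 3.6 of 10 cases
- m = 0.30: 0.40 × 0.7 = 0.28, or 2.8 of 10 cases
- m = 0.50: 0.40 × 0.5 = 0.20, or 2.0 of 10 cases

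So 4 true relapsing cases among 10 appear as about 2 to 4. In the mildest scenario almost nothing changes.

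**Chance of recording no relapse at all in 10 cases.** This is (1 − p(1 − m))^10. With p = 0.30:

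- full capture: 0.70^10 = 2.8%
- m = 0.10: 0.73^10 = 4.3%
- m = 0.30: 0.79^10 = 9.5%
- m = 0.50: 0.85^10 = 19.7%

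**Effect on a before/after comparison.** Let s be the share of events captured in each period. If the illness truly does not change, observed post/pre ratio = s(post) ÷ s(pre).

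- equal capture: 1.0
- 90% before, 50% after: 0.5 ÷ 0.9 = 0.56 (false improvement)
- 50% before, 90% after: 0.9 ÷ 0.5 = 1.8 (false worsening)

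In addition, the prior variable counts admissions only, while the later one also takes in emergencies. That difference alone pushes towards apparent worsening.

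**The case against.** The strongest reply is that the protocol does not say what a reader might infer from it.

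- **Where records are searched.** A reader might infer that only the bariatric centre's records are reviewed. The centre databases are named for identifying patients. The record review has no stated limit and may reach psychiatric or shared records. This stands: a restriction to the centre is not in the text. What remains is that nothing requires wider records to be seen or documents that they were.
- **How unseen events are coded.** A reader might infer that an outside event is entered as zero. No such rule is written, a count can be left blank or coded missing, and the protocol requires entries to agree with source documents. This also stands. But a reviewer who finds no event has no prompt to ask whether the right record was open.
- **Direction.** A reader might infer that the error always favours surgery. That holds only for the absolute post-surgery frequency, and only if unknowns are counted as none. A before/after result can move either way, and the controls, who have no psychiatric pathology, offer no relapse comparison.
- **Patients who have left the centre.** Loss to follow-up is recorded, so they can be flagged, and the sentence expecting them is about consent. This is fair, but it does not help with a patient who stays at the centre and is admitted elsewhere.
- **Left to the analysis plan.** Coding rules often are. Which facts are abstracted from the records is not: an analysis plan cannot recover a date or a site that was never collected.

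**Conclusion.** The point holds in conditional form. The protocol fixes relapse as an event count from a record review of unstated scope and collects nothing that shows whether, where or until when psychiatric records were visible. Events outside the reviewed records may be missed, and a missed event would look like no relapse.

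If such events are counted as none, the absolute post-surgery relapse frequency is biased downwards: from an assumed 40% to between 36% and 20% for assumed losses of 10% to 50%. The actual size cannot be known from the protocol. The documents do not support the stronger statement that relapses elsewhere *are* entered as zero, nor that the psychiatric result *must* look too good.

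The outcome is secondary and descriptive; the weight-loss comparison is unaffected. This is an inexpensive improvement worth making before data collection, not a fault that undermines the study.

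**What to change.** Add two items per case to the data collection notebook:

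1. Site of psychiatric care and whether its record was seen (own centre; elsewhere, seen; elsewhere, not seen; unknown).
2. Last date to which a psychiatric record was seen.

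Then state in Methods that:

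- relapse is coded *not known* where no psychiatric record was seen;
- relapses are counted up to the date in item 2 and reported per person-time observed, with the number of cases not known beside the result;
- any before/after comparison uses the same event definition in both periods.

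List incomplete capture of outside events among the limitations.

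The cost is two columns, a short addition to Methods and a line in the limitations. The relapse denominator becomes smaller, which is felt if the cases number near the minimum of 10. Cases with a psychiatric record seen may also differ from those without, so some selection is possible. Reporting the number not known lets the reader judge that.
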